10.6.3. Secondary Endpoint(s)

For the viral shedding of SARS-CoV-2 endpoint, a linear regression model with an indicator variable for the treatment group and additional pre-specified covariates will be applied. Analytic details about other secondary endpoints will be included in the Statistical Analysis Plan.

The statistical comparisons of the randomized arms with respect to the SAEs and EOSI interest will use chi-square or other appropriate 2-sample methods. Analysis of all-cause mortality will be conducted using a log-rank test with event curves presented as Kaplan-Meier estimates. A Cox proportional hazards will be used to estimate the hazard ratio associated with the HCQ intervention. Analyses of all-cause and cause-specific hospitalizations will use similar strategies.

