2.3.2. Benefit Assessment

Participants who randomize to the treatment group may benefit from the prophylactic study drug administration. There is no direct benefit to participants randomized to the control group apart from participating in generating evidence that may ultimately support preventative therapy for SARS-CoV-2 infection. Participants will receive information about the best personal protective measures to prevent SARS-CoV-2 infection. In addition, they will benefit from involvement with the team following their health status during the study. The knowledge gained will be a benefit to others in the future. This is an opportunity to answer important questions for public health and prevention of SARS-CoV-2 infection for HCWs. Clarifying the adverse effect profile of HCQ in HCWs will also inform the public taking HCQ for prophylaxis of SARS-CoV-2 infection and potentially treatment of COVID-19.

3. Objectives and Endpoints

Objectives	Endpoints
Primary	
To evaluate the efficacy of HCQ to prevent COVID-19 clinical infection in HCWs	 Clinical infection with COVID-19: Confirmed: new-onset of fever or cough or dyspnea AND confirmed COVID-19 positive test result via local PCR testing, OR Suspected: new-onset fever or cough or dyspnea without local PCR testing due to local restrictions and/or testing policies
Secondary	
 To evaluate the efficacy of HCQ to prevent viral shedding of SARS-CoV-2 among HCWs Evaluate safety and tolerability of HCQ 	 Viral shedding of SARS-CoV-2: Central lab confirmed COVID-19 test Safety and tolerability as determined by weekly DSMB assessment of subject reported serious adverse events (SAEs) and HCQ-associated Events of Special Interest (Section 9.1.4)
Exploratory	
 Evaluate SARS-CoV-2 seroconversion in participants taking HCQ Describe COVID-19 infectious complications in participants taking HCQ Describe time off from work for medical reasons in participants taking HCQ Describe QoL 	 Seroconversion at 1 month COVID-19 complications: hospitalization ICU level care or ventilation Days sick or lost work-time Patient-Reported Outcomes Measurement Information System (PROMIS) Emotional Distress-Anxiety-Short Form, a Single Item Burnout Measure, Patient Health Questionnaire (PHQ-2)
Describe experience of household contacts	Patient-reported clinical infections among household contacts and other impacts on household

4. Study Design

Refer to Section 1.2 for the Study Schema.

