10.1.2. Secondary Hypotheses

- Allocation to HCQ results in prevention of viral shedding of SARS-CoV-2 among HCWs at risk for COVID-19 infection.
- Hydroxychloroquine administration will be safe and well tolerated.

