10.2. Sample Size Determination

The sample size of approximately 2,000 randomized participants was selected to yield reasonable power for testing the primary outcome of clinical infection with COVID-19. Several design factors and research objectives have been considered in developing an appropriate sample size for the HERO-HCQ study.

Based on several recent randomized clinical trials studying HCQ for inpatient COVID-19 disease conditions, a reduction in the clinical infection risk by a relative 50% is considered a clinically important treatment effect. For the primary outcome of clinical infection of COVID-19, the sample size will provide 80% power to detect a 50% relative decrease in the risk for the intervention group compared to usual care assuming that the placebo group risk is 5%. Similarly, the proposed sample size will provide 80% power to detect a difference of 6.5% (active) vs. 10% (placebo). These calculations assume a two-sided Type I error rate of 0.05 with 1:1 randomization and are based on a two-group continuity corrected chi-square test.

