10.6.1. General Considerations

Statistical comparisons will be performed using two-sided significance tests. Baseline demographic and clinical variables will be summarized for each randomized arm of the study. Descriptive summaries of the distribution of continuous variables will be presented in terms of percentiles (e.g., median, 25th and 75th percentiles) along with means and standard deviations. Categorical variables will be summarized in terms of frequencies and percentages.

The primary endpoint is clinical infection with COVID-19. Individual participants are expected to receive study drug for 30 days and will be followed for another 30 days for clinical events and patient-reported outcomes. Data collected during the 60-day follow-up will be included in the primary analyses.

Participants that develop symptoms of COVID-19 will follow local clinical and/or employee health protocols for testing and management. If testing is done per protocol, the results will be used for confirmation of the primary outcome. However, in some regions, testing may not be done for individuals with suspected COVID-19 symptoms and low risk factors for severe disease. Instead, these individuals may be told to self-isolate and monitor symptoms in lieu of testing. To reflect the different approaches expected for testing and management of healthcare workers who develop symptoms of COVID-19, the primary outcome includes both confirmed and suspected clinical COVID-19 infections.

The primary endpoint will be tested at the two-sided 0.05 level. All secondary endpoints will be tested at the 0.05 level.

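### The safety hypothesis cannot be established by the only SAE/EOSI comparison the protocol names, a two-sided 0.05 difference test; an interval for the risk difference should carry the conclusion

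*Protocol*

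**What the plan says.** Section 10.1.2 of the protocol, under the statistical hypotheses, contains the statement "Hydroxychloroquine administration will be safe and well tolerated". No acceptable excess risk accompanies it.

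Section 3 makes safety a secondary endpoint, worded as "Safety and tolerability as determined by weekly DSMB assessment of subject reported serious adverse events (SAEs) and HCQ-associated Events of Special Interest". Section 10.6.1 sets the general rules: "Statistical comparisons will be performed using two-sided significance tests", and "All secondary endpoints will be tested at the 0.05 level". Section 10.6.3 names the method for the events themselves: "The statistical comparisons of the randomized arms with respect to the SAEs and EOSI interest will use chi-square or other appropriate 2-sample methods". The same section plans a log-rank test, Kaplan-Meier curves and a Cox hazard ratio for all-cause mortality, with similar methods for hospitalizations. It leaves further detail on secondary endpoints to the statistical analysis plan.

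Section 10.5 bases safety analyses on all randomized participants. Section 10.2 ties the size of the trial to efficacy alone: "The sample size of approximately 2,000 randomized participants was selected to yield reasonable power for testing the primary outcome of clinical infection with COVID-19". Section 9.1.3 lets the DSMB judge whether an SAE is clearly commoner on HCQ and should be reported to the FDA.

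**The concern.** The hypothesis and the test do not fit each other. The null hypothesis of a chi-square or other two-sample comparison is that the arms do not differ. Rejection in the direction of harm counts against the hypothesis. Failure to reject leaves it undecided, because the same result arises when the drug is harmless and when events are too few to show a harm. No result of the named comparison can support the statement in 10.1.2.

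Efficacy is treated differently. Section 10.6.2 makes the difference in proportions with its 95% confidence interval the main summary of the treatment effect. SAEs and EOSIs are given only a test.

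The participants are working people without diagnosed COVID-19 who take a preventive drug, and section 2.3.2 expects the adverse-effect findings to inform public use of HCQ. A safety statement resting on a non-significant result could reassure when the data are still compatible with a several-fold excess.

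**Working it through.** **Inputs.** About 2,000 randomized 1:1, so 1,000 per arm, all in the safety population (10.2, 10.5). Two-sided 0.05 (10.6.1). Chi-square, or Fisher's exact test as an alternative two-sample method (10.6.3). The protocol gives no SAE or EOSI rate, so the placebo rates below are assumptions, shown over a range.

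**The plan's own figure.** Section 10.2 claims 80% power for 5% vs 2.5% with a continuity-corrected chi-square test.

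- Uncorrected: n = [1.96·√(2p̄q̄) + 0.8416·√(p₁q₁ + p₂q₂)]² / (p₁ − p₂)². With p̄ = 0.0375 this is (0.5266 + 0.2256)² / 0.000625 ≈ 905.4, so 906 per arm.
- Corrected: n′ = (n/4)·[1 + √(1 + 4/(n·0.025))]² ≈ 984 per arm, or 1,968 in total. Power at 1,000 per arm is 80.7%.
- The second scenario, 10% vs 6.5%, needs 1,026 per arm (2,052 in total), with 79.0% power at 1,000 per arm.

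Both reproduce to rounding. No corresponding figure is given for safety.

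**Chance of missing a true excess.** For each pair of true rates, the binomial probabilities of all count pairs (1,000 per arm) with p ≤ 0.05 in the direction of harm were summed. The miss rate is one minus that sum.

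| Placebo vs HCQ | Chi-square | Fisher |
|---|---|---|
| 0.1% vs 0.2% | 95% | 99% |
| 0.5% vs 1% | 76% | 82% |
| 1% vs 2% | 54% | 62% |
| 2% vs 4% | 24% | 29% |
| 2.5% vs 5% | 15% | 18% |
| 0.5% vs 1.5% | 36% | 46% |
| 0.5% vs 2% | 11% | 16% |
| 1% vs 3% | 9% | 12% |
| 2% vs 5% | 4% | 5% |

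For a doubling, the miss rate falls to 50% at a placebo rate of about 1.1% (chi-square) or 1.3% (Fisher). By the uncorrected formula, 80% power for a doubling would need 2,319 per arm at 1% and 4,673 per arm at 0.5%.

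**What a non-significant result can hide.** Take 13 events on HCQ and 5 on placebo, 1,000 per arm.

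- Chi-square = 2000·(13·995 − 5·987)² / (1000·1000·18·1982) = 3.59, p = 0.058. Fisher p = 0.095.
- Wilson limits: 0.761% to 2.211% for 13/1000, and 0.214% to 1.165% for 5/1000.
- Newcombe lower limit for the difference: 0.80 − √[(1.3 − 0.761)² + (1.165 − 0.5)²] = −0.06 percentage points.
- Newcombe upper limit: 0.80 + √[(2.211 − 1.3)² + (0.5 − 0.214)²] = +1.76 percentage points.
- Score interval for the risk ratio: 0.97 to 6.98.

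With equal counts of 5 and 5, the Newcombe limits are ±√(0.665² + 0.286²) = ±0.72 points, and the score upper limit of the risk ratio is 3.2.

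**The case against.** The strongest reply is that section 10.6 is a summary, that 10.6.3 defers detail on other secondary endpoints to the analysis plan, and that intervals for adverse-event differences are ordinary content of such a plan. That stands as far as a missing interval goes: the analysis plan is not at hand, and the wording of 10.6.3 does not rule an interval out. It does not remove the mismatch, because the protocol itself fixes the hypothesis, the significance level and the family of tests.

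A reader might infer that the protocol treats p > 0.05 as proof of safety. No section says so. Section 3 rests safety on DSMB assessment, and section 9.1.3 relies on DSMB judgement, not on a 0.05 test. That assessment serves monitoring and reporting during the trial, however; it states no bound on excess risk that a final conclusion could use.

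A reader might also infer that serious harms get no effect estimate at all. That is not so. Death and inpatient hospitalization are SAE criteria in section 9.1, and hazard ratios are planned for both. The gap concerns SAEs as a class and the EOSIs.

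Finally, low power for rare harms is common in a trial sized on efficacy, and two-sample safety comparisons are conventional. Both are true. The point is what the result may be said to show.

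**Conclusion.** The point holds as a mismatch between a stated hypothesis and the stated test. It does not depend on any event rate: a test of no difference cannot establish that HCQ is safe and well tolerated.

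The size of the risk does depend on the rate, which the protocol does not give. At 1,000 per arm and two-sided 0.05, a doubling is missed more often than not only below a placebo rate of about 1.1% (chi-square) to 1.3% (Fisher). At 2% it is detected 76% or 71% of the time. The general statement that a doubling would usually be missed therefore goes too far, and larger excesses such as 1% vs 3% are mostly detected. Rates below 1% are a reasonable assumption for individual HCQ-related events in section 9.1.4 such as aplastic anemia or hepatic failure, but remain an assumption. Fever, listed there among the other events of interest, need not be rare.

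This is a cheap improvement to the safety wording. It does not touch the primary analysis.

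**What to change.** - **Section 10.1.2:** replace the safety hypothesis with an aim to estimate the HCQ-minus-placebo difference in the risk of any SAE and of any HCQ-associated EOSI.
- **Section 10.6.3:** make the risk difference with a two-sided 95% confidence interval suited to small counts (Newcombe or score) the basis of the safety conclusion for both, worded by the upper limit, that is, the largest excess the data exclude. Report individual EOSIs descriptively. Any p-values serve only as flags for harm.
- **Section 10.6.1:** exempt safety from the statement on 0.05-level testing, and say that non-significance will not be taken as evidence of safety.

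The cost is wording in three sections and one added column in the safety tables, with no new data or participants. The downside is that the trial could claim only that an excess above a stated size is excluded, not that HCQ is safe and well tolerated.

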10.6.4. Exploratory Analysis

Details of the exploratory analyses will be described in the Statistical Analysis Plan.

10.6.5. Subgroup Analyses

In addition to analyses of secondary outcomes in Section 10.6.3, a set of analyses will be reported to explore whether intervention effects on the primary and secondary outcomes are consistent across subgroups of interest defined according to baseline characteristics. These subgroups will be specified in the Statistical Analysis Plan. The planned sub-groups will include age, sex, race/ethnicity, occupation, and COVID-19 risk factors.

For each subgroup analysis, a logistic regression model (or linear model) will be used that is similar to the one described above, but with additional terms identifying subgroup membership and the intervention by subgroup interaction.

10.6.6. Adherence and Retention Analysis

Treatment dropouts and consent withdrawals will be tracked by verifiable means at each follow-up assessment. Participants will be asked about their use of study drug during telephone follow-up. Those reporting discontinuation or switching will be asked about the reasons for discontinuation/switching.

Because study participants are HCWs, it is expected that this study will have excellent retention. Measures of study retention to inform follow-up time will be based on a number of measures, weekly web-based check-ins for symptoms and exposure history or in-person visit.

10.7. Interim Analyses

Regular DSMB reviews will be conducted to ensure the safety of study participants and evaluate the accumulating endpoint data by treatment group. Regular DSMB meetings will monitor the following parameters at a minimum:

- Recruitment progress
- Enrollment overall and by subgroups
- Adherence, retention, and status of data collection
- Events of special interest
- Unanticipated problems
- Serious adverse events (SAEs)

Interim examination of clinical endpoints will be based on the accrual of primary endpoint data. It is expected that reviews of the data will occur approximately weekly following the enrollment of the first participants.

For ethical reasons, interim examinations of key safety and process data will be performed at regular intervals during the course of the trial. The DCC will create reports to track participant enrollment, rates of adherence with the assigned treatment strategy, and frequency of protocol violations. Prior to each meeting, the DCC will conduct any requested statistical analyses and prepare a summary report along with the following information: participant enrollment reports, rates of adherence with the assigned treatment, and description of SAEs.

Safety reports will be prepared for the DSMB approximately weekly once enrollment begins. For futility monitoring, HERO-HCQ will employ a flexible approach based on the prediction interval methods of Evans, Li, and Wei. [48] These flexible methods allow for the assessment of treatment differences as well as the precision related to those estimates. The futility reviews may include predicted interval plots as a tool to summarize the information. To implement these methods, we will predict the confidence intervals at the end of the study conditional on a range of reasonable assumptions including the null hypothesis, the alternative hypothesis, and the observed trend. The upper and lower limits of these prediction intervals will be compared with 'acceptable' treatment group differences that allow for the incorporation of other information including the safety profile of the intervention. It is expected that the first futility assessment will occur once the first 1000 randomized participants have completed their 30-day visit. Additionally, conditional power calculations will be used to assess the futility of continuation in the presence of a small or negative treatment effect.

The method of Haybittle and Peto will be proposed as the primary guide for interpreting interim efficacy analyses. [49, 50] The four interim efficacy analyses are expected to occur after the first 1000, 1250, 1500, and 1750 participants have completed their 30-day visits. The proposed efficacy monitoring guideline uses large critical values ($p \le 0.001$) for the treatment group comparison of the outcome of clinical infection with COVID-19 at each assessment until the planned final analysis. A two-sided stopping boundary for all-cause mortality with p < 0.001 will be recommended for all reviews.

Monitoring boundaries are intended to guide the interpretation of interim analyses and are not a strict rule for early termination. It is expected that both internal and external factors will

influence the decisions of the DSMB. The Statistical Analysis Plan will describe the planned interim analyses and futility monitoring in greater detail.

10.8. Data Safety Monitoring Board (DSMB)

The DSMB will monitor participant safety and study performance. A DSMB charter that outlines the operating guidelines for the committee and the procedures for the interim evaluations of study data will be developed by the DCC and agreed upon by the DSMB. Reports will be prepared by the DCC in accordance with the plan outlined in the charter, or as requested by the DSMB chair, and will include interim analyses of primary and secondary endpoints, additional safety events, and other information as requested by the committee. After each scheduled closed meeting, the DSMB will send a recommendation to the IND sponsor to continue, modify, or terminate the study. After approval, the recommendations will be forwarded by the CCC to investigators for submission to their local, regional and national IRB/Ethic Committees, as applicable. DSMB reports will be the primary mechanism for reporting safety concerns to FDA, as needed. The DSMB will establish links with the FDA and other appropriate DSMBs as possible to ensure rapid communication of important safety findings as needed. Please refer to the DSMB Charter for further details.

11. Ethical Standards

11.1. Institutional Review Board (IRB)

The protocol, ICF(s), recruitment materials, and all participant materials will be submitted to the IRB(s) of record for review and approval. This approval must be obtained before any participant is enrolled. Any amendment to the protocol will require review and approval by the IRB(s) before being implemented in the study. All changes to the consent form will also be IRB-approved and a determination will be made regarding whether previously consented participants need to be re-consented.

11.2. Informed Consent Process

Consent forms describing in detail the study agent, study procedures, and risks are given to the participant and documentation of informed consent is required prior to starting study procedures. Informed consent is a process that is initiated prior to the individual's agreeing to participate in the study and continues throughout the individual's study participation. Extensive discussion of risks and possible benefits of participation will be provided to the participants. Consent forms will be IRB-approved and the participant will be asked to read and review the document. The investigator (or their delegate) will explain the research study to the participant and answer any questions that may arise. All participants will receive a verbal explanation in terms suited to their comprehension of the purposes, procedures, and potential risks of the study and of their rights as research participants. Participants will have the opportunity to carefully review the written consent form and ask questions prior to signing.

The participants should have the opportunity to discuss the study and think about it prior to agreeing to participate. The participant will sign the informed consent document prior to any procedures being done specifically for the study. The participants may withdraw consent at any time throughout the course of the study. A copy of the informed consent document will be given to the participants for their records. The rights and welfare of the participants will be protected by emphasizing to them that the quality of their medical care will not be adversely affected if they decline to participate in this study.

The study team will distinguish between the desire to discontinue study drug and the desire to withdraw consent for study follow-up. In the event that a participant withdraws consent, the investigator or his designee will clarify with the participant and document whether the withdrawal is a temporary or permanent, and if a full or partial withdrawal.

11.3. Participant and Data Confidentiality

Participant confidentiality is strictly held in trust by the participating investigators, their staff, and the sponsor(s) and their agents. This confidentiality is extended to cover testing of biological samples in addition to the clinical and private information relating to participants. Therefore, the study protocol, documentation, data, and all other information generated will be held in strict confidence. No information concerning the study or the data will be released to any unauthorized third party without prior written approval of the sponsor. The study participant's contact information will be securely stored in the clinical study database.

Study participant research data, which is for purposes of statistical analysis and scientific reporting, will be transmitted to and stored at Duke Clinical Research Institute. The study data entry and study management systems used by clinical sites and by research staff will be secured and password protected. At the end of the study, all study databases will be de-identified and archived.

